### 12.22 Quality of life

Difference in the World Health Organization Quality of Life – BREF scores (WHOQOL-BREF). The 26-item questionnaire is a validated, self-report instrument that assesses 4 domains of quality of life: physical health (7 items), psychological health (6 items), social relationships (3 items) and environment (8 items). There are also 2 items that measure overall quality of life and general health. The questionnaire takes 15-20 minutes to complete. The questionnaire prefaces each item, “Think about your life in the last two weeks..”. The responses are on a 5-point Likert scale, ranging from 1=not at all/very dissatisfied/never/very poor to 5=very good/very satisfied/an extreme amount/extremely/completely/always, depending on the item. The questionnaire is valid, reproducible, relevant to both healthcare providers and patients with OUD, and has been shown to be responsive to changes in quality of life across cultures, geography and etiology.

### 12.23 Clinic retention

Difference in proportion of patients who attend  $\geq 80\%$  of scheduled clinic visits, where a **clinic visit is defined as a scheduled visit with a RAAM clinic healthcare provider for any reason, including urine drug testing, medication administration, or counselling**. Clinic retention is the most commonly reported outcome measure in opioid substitution trials, with 46% reporting it as an outcome. However, there is no “gold standard” definition of retention, with over 16 different methodologies used to measure retention in 28 trials of opiate substitution therapy. The number of clinic visits any patient will be assigned will include those scheduled as part of the trial and any other visits scheduled at the discretion of the RAAM clinic healthcare providers. The measure of clinic retention used in this trial is valid, objective, reproducible, relevant to both healthcare providers and patients with OUD, and has been shown to be responsive to opiate substitution therapies in previous studies.

### 12.24 Mortality

Difference in mortality proportions, where **mortality is defined as any death attributable to opioid use regardless of the intent**. Opioid-related deaths continue to increase year after year and have emerged as a public health crisis. Only 2 previous opiate substitution treatment studies measured mortality as an outcome, the latest published in 1980. The method used by the Canadian Institute for Health Information will be used to measure mortality in this study given its validity, reproducibility, importance to both healthcare providers and patients with OUD, and its responsiveness to opiate substitution therapies.

# 13 Participant timeline

			Study Period (Weeks)																											
			-1	0	T1	T2	T3	T4	T5	T6	T7	T8	T9	T10	T11	T12	T13	T14	T15	T16	T17	T18	T19	T20	T21	T22	T23	T24		
Activity	C R F	M R P	w-1	w0	w2	w4	w6	w8	w10	w12	w14	w16	w18	w20	w22	w24	w26	w28	w30	w32	w34	w36	w38	w40	w42	w44	w46	w48		
Enrollment																														
Expressed Consent	N	HCP	X																											
Eligibility Screen	Y	HCP SC	X																											
Informed Consent	N	HCP SC	X																											
Randomization	Y	SC		X																										
Demographics	Y	HCP		X																										
Pregnancy test	Y	HCP	X																											
EKG	Y	HCP	X																											
Bloodwork	Y	HCP	X																											
Interventions																														
Suboxone®	Y	HCP		X																										
Sublocade®	Y	HCP		X		X		X		X		X		X		X		X		X		X		X		X		X		
Counselling	Y	HCP		X	X	X	X	X		X		X		X		X		X		X		X		X		X		X		
RAAM clinic visit	Y	HCP		X	X	X	X	X		X		X		X		X		X		X		X		X		X		X		
Pre-clinic visit phone call	Y	HCP SC		X	X	X	X	X		X		X		X		X		X		X		X		X		X		X		
Assessments																														
General exam	Y	HCP		X	X	X	X	X	X	X	X	X	X	X	X	X	X	X	X	X	X	X	X	X	X	X	X	X	X	X
Urine drug test	Y	HCP	X	X	X	X	X	X	X	X	X	X	X	X	X	X	X	X	X	X	X	X	X	X	X	X	X	X	X	X
Timeline Followback	Y	HCP	X	X	X	X	X	X	X	X	X	X	X	X	X	X	X	X	X	X	X	X	X	X	X	X	X	X	X	X
MSQ	Y	HCP SC					X			X			X			X			X			X			X			X		
WHOQOL-BREF	Y	HCP SC		X						X						X						X								X
Pregnancy test	Y	HCP				X		X		X		X		X		X		X		X		X		X		X		X		
SAE	Y	HCP		X																										
EKG	Y	HCP																												
Bloodwork	Y	HCP																												

CRF=case report form; MRP=most responsible person; N=No; Y=Yes; HCP=healthcare provider; SC=study coordinator; EKG=electrocardiogram; MSQ=medication satisfaction questionnaire; WHOQOL-BREF=Quality of life questionnaire; SAE=severe adverse event

## 14 Sample size

### 14.1 Rationale

The sample size was calculated on the basis of the primary hypotheses. In the three previous comparative effectiveness studies between Suboxone® and Sublocade® (Table 1), the primary outcomes were non-inferiority with an upper margin of difference in opioid positivity of < 15%. None of these trials involved Canadian patients attending RAAM clinics. As previously reviewed, given the significant differences in costs of Sublocade® compared to Suboxone® and the absence of evidence of cost-effectiveness of Sublocade® compared to Suboxone® in the Canadian healthcare system, it would be important to demonstrate to healthcare providers who advise patients that must pay out-of-pocket for their medications that the increased cost of Sublocade® provides clinically significant benefits to important patient-centered outcomes over those of less expensive OAT. In addition, it would be important to demonstrate the same benefits to policy makers and insurers of the superiority of Sublocade® compared to Suboxone® not only in reducing rates of opioid positivity but also healthcare utilization that might offset the cost differential of the two drugs and provide the rationale to promote Sublocade® as an insured first line agent for OUD. As such, a clinically important difference in opioid positivity has been selected as  $\geq 15\%$  difference for Sublocade® compared to Suboxone® given that previous studies had used this threshold as the upper margin for non-inferiority. As for healthcare utilization, CADTH estimated that a 73% reduction in cost of Sublocade® would be needed to make it cost-effective for the Canadian healthcare system (see Section 5.14). Given the current cost for a 12-month treatment of Sublocade® in Canada is \$6600, a 73% reduction would translate into an annual cost of \$1782, a cost reduction of \$4818. The average cost of healthcare utilization in Ontario for an opioid-related harm or poisoning was \$9626 (Section 5.12). To recoup the drug costs from a reduction in healthcare utilization costs would require at least a 50% reduction in healthcare utilization over a 12-month period. As such, a clinically important difference in healthcare utilization has been selected as  $\geq 50\%$  difference for Sublocade® compared to Suboxone®. All sample size estimations were conducted using nQuery version 8.7.2.0 ([nQuery | Platform for optimizing trial design \(statsols.com\)](https://www.statsols.com/)); accessed November 17, 2021).

### 14.2 Opioid positivity

Previous studies have used a simple data generating model for opioid positivity in which the difference in proportions of opioid positivity, regardless of how opioid positivity was defined, never accounted for the clustering of repeated measures of opioid positivity by individual and site. This dramatically reduces the power to detect differences in proportions of opioid positivity between treatment groups. For example, for our trial to detect a difference in proportion of RFWs of  $\geq 0.15$  with a power of 80% using a Z-test (unpooled variance) significance level at the 2-sided  $\alpha$  level of 0.05 would require 160 patients per group if the comparator group's RFWs proportion is 0.3 (estimated from Lofwall *et al.*). Contrast this to a

data generating model that more appropriately accounts for clustering of opioid positivity observations. In this study, a mixed model using a 3-level hierarchical design will be used to describe the relationship between repeated measures of opioid positivity (Level 1) obtained from individual patients (Level 2) recruited from 4 different RAAM clinic sites (Level 3), where Level 2 patients will be randomized to either Sublocade® or Suboxone®. In addition to the assumption of a comparator group RFWs proportion of 0.3, if we also assume a Level 1 unit correlation of 0.8, a Level 2 correlation of 0.025, and an average of 5 repeated measures of opioid positivity per Level 2 patient over the study period, then we would need only 34 patients per treatment group to detect a difference in RFWs proportion of  $\geq 0.15$  with a power of 80% and a mixed model test significance level at the 2-sided  $\alpha$  level of 0.05. Sensitivity analysis using different values for the variables used in the hierarchical model assumptions (Table 3) demonstrates that the upper range of sample sizes is consistently less than 70 per group.

**Table 3: Sensitivity analysis for sample size estimations needed to detect  $\geq 15\%$  difference between RFWs proportions between treatment groups for a mixed model test in a 3-level hierarchical design (Level 2 randomization)**

Variable 	Scenario 									
	1	2	3	4	5	6	7	8	9	10
Power	80	80	80	80	80	80	80	80	90	90
Comparator group RFW proportion	0.3	0.3	0.3	0.3	0.1	0.6	0.3	0.3	0.3	0.3
Level 1 unit correlation	0.8	0.5	0.99	0.99	0.99	0.99	0.8	0.8	0.99	0.99
Level 2 unit correlation	0.025	0.025	0.1	0.001	0.001	0.001	0.025	0.025	0.001	0.001
Level 3 units	4	4	4	4	4	4	3	2	4	3
Average number of Level 1 units per Level 2 units	5	5	5	5	5	5	5	5	5	5
Sample size per group	34	24	37	41	42	38	45	68	41	54

 Assumptions: 2-sided  $\alpha$  level of 0.05; Difference in RFWs proportion  $\geq 0.15$ ; Treatment group allocation = 1:1

 Highlighted cells (Yellow) represent changes from preceding scenario

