**Table 1: Summary of comparative effectiveness of extended-release versus immediate release buprenorphine**

Author (Country/year)	Buprenorphine		Time Period (weeks)	Primary Outcome	Effect size (extended vs immediate) (mean difference (95% CI))
	Extended (N)	Immediate (N)			
Rosenthal et al. (USA/2013)	Implants (4 x 80mg) (N=114)	SL-BPN/NX (12- 16 mg/d) (N=119)	24	Mean % negative uds  + self-report opiod use (weeks 1 to 24)	31% vs 33.1% (-2.1 (-10.7, 6.2))
Rosenthal et al. (USA/2016)	Implants (4 x 80mg) (N=84)	SL-BPN/NX (≤8 mg/d) (N=89)	26	Responder proportion 	96.4% vs 87.6% (8.8% (0.009, ∞))
Lofwall et al. (USA/2018)	SC-BPN (8-32 mg/week) (weeks 1-11) SC-BPN (64-160 mg/month) (weeks 12-24) (N=215)	SL-BPN/NX (4- 24 mg/d) (weeks 1-11) SL-BPN/NX (8- 32 mg/d) (weeks 12-24) (N=213)	24	Mean % negative uds + self-report opiod use  Responder proportion 	35.1% vs 28.4% (6.7% (-0.1, 13.6))  37.0% vs 31.0% (3.0% (-4.0, 9.9))

 uds=urine drug screen; missing uds imputed as positive; denominator was 72 uds (3 per week x 24 weeks)

 responder proportion defined as participant with ≥4 of 6 months with negative uds + negative self-report (uds + self-report scheduled every month plus 4 random uds; total 10 uds + self-reports); all patients had been on SL-BPN/NX ≥ 12 months prior to enrollment; missing uds imputed as positive or negative with a 20% penalty for positive in extended-release group

 responder proportion defined as participant with  $\geq 2$  weeks uds/self-report negative of weeks 9-11 + uds/self-report negative at week 12, plus  $\geq 5$  weeks uds/self-report negative of weeks 12-24 + uds/self-report negative from weeks 21-24; missing uds imputed as positive

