## 12 Outcomes

### 12.1 Primary outcome measures

#### 12.11 Opioid positivity

Difference in proportions of relapse-free weeks (RFWs) at 12-months from the date of randomization, where ***relapse-free weeks are defined by the cumulative number of weeks alive during the study period in which there was a negative urine drug screen and negative self-report for non-prescribed opioids.*** The potential number of RFWs for each patient is the cumulative number of weeks that the patient is alive during the 12-month study period, with a maximum of 48 weeks. A week is defined as a consecutive 7-day period starting on the day of the week that randomization occurred. A patient is considered to have 'completed' a week as long as they are alive for  $\geq 1$  day of that week. For example, if a patient is randomized on a Tuesday, and subsequently dies on a Thursday of the 32nd week, the patient will have been considered to have been alive for 32 weeks. The denominator used in estimating the proportion of RFWs will be the total number of weeks that the patient was alive during the study period. Vital statistics for all participants (date and year of death) will be available through linkage with the Office of the Registrar General of Ontario database. The cumulative number of RFWs alive will be used as the numerator in estimating the proportion of RFWs. Scheduled urine drug testing and self-reports will occur every 2 weeks during the study period starting in week 2 from randomization. Imputation of missing data will occur for those weeks in which a urine drug screen/self-report was not scheduled according to the results of the subsequent week's urine drug screen/self-report. For example, if a urine drug screen/self-report was not scheduled for week 11, but a scheduled urine drug screen/self-report was done on week 12 and week 12 met the criteria for a RFW, then week 11 would be imputed as a RFW (Figure 1). Similarly, for weeks with scheduled urine drug screen/self-reports that are missed, that week and the preceding week in which there was no scheduled urine drug screen/self-report will not be counted as RFWs (for example, see Figure 1, week 17 and 18). In the hypothetical patient represented in Figure 1, 20 urine drug screens/self-reports were completed, with 5 positive and 15 negative urine drug screens/self-reports, resulting in 30 cumulative RFWs over the 48-week study period, or a proportion of RFWs of 0.625.

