#### 14.4 Final sample size

In a hierarchical 3-level mixed effects model with 45 and 45 level 2 units (RAAM clinic patients) randomized to Suboxone® and Sublocade® in a 1:1 ratio, 4 level 3 units (RAAM clinics) in total and an average of 5 level 1 units (RFWs) per level 2 unit, 90.0% power is achieved to detect a difference in RFWs proportions of at least 0.15, where the Suboxone® and Sublocade® RFWs proportions are 0.3 and 0.45, respectively, assuming that the correlation between level 1 units in a level 2 unit is 0.8 and the correlation between level 2 units in a level 3 unit is 0.025, and the 2-sided test is performed at the 5% significance level. Using even a much smaller sample size (N=20 patients per group with 50% loss-to-follow-up over 12-month study period), a 2-sided comparison of two incidence rates (number of healthcare days per 1000 patient days exposure) with a sample size of 3650 patient days exposure per group would achieve 99% power at the 0.05 significance level to detect a difference in incidence rates of at least 1 if the Suboxone® group incidence rate was 2.

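### The stated 90.0% power for opioid positivity at 45 patients per arm is not reached on any variability input the documents support; the range is about 37% to 58%

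*Combined protocol and SAP*

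**What the plan says.** Section 14.2 of the combined protocol and SAP first gives 160 patients per group for a simple Z-test. It then moves to a three-level model, for which the planners "assume a Level 1 unit correlation of 0.8, a Level 2 correlation of 0.025, and an average of 5 repeated measures of opioid positivity" per patient, and arrives at 34 per group for 80% power.

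Section 14.4 fixes 45 patients per arm. It takes "an average of 5 level 1 units (RFWs) per level 2 unit" and the same two correlations, and says that "90.0% power is achieved to detect a difference in RFWs proportions of at least 0.15". The assumed "RFWs proportions are 0.3 and 0.45, respectively", and "the 2-sided test is performed at the 5% significance level".

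The comparator proportion of 0.3 is attributed to the weekly/monthly depot trial in Table 1. No source is given for the 0.8 or the 5. Table 3 tries correlations of 0.5, 0.8 and 0.99 but keeps 5 measures in all ten scenarios.

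Section 12.11 sets a different test count: "Scheduled urine drug testing and self-reports will occur every 2 weeks during the study period starting in week 2 from randomization". In the section 13 timeline, the urine-test and self-report rows run from week 2 to week 48, which is 24 occasions. Missed tests are scored as not relapse-free, so they do not reduce the count while a patient is alive.

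**The concern.** Repeated measures that correlate at 0.8 within a patient add little information, so a fall from 160 to 34 per group is implausible on its face. The variability inputs are also unanchored. The plan borrows the depot trial's mean but not its spread, although Table 1 prints confidence intervals from which a per-patient SD can be recovered.

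Opioid positivity is one of two primary outcomes, and section 14.1 sets 0.15 as the smallest clinically important difference. If true power at 0.15 is near one half or lower, a null result would say little about whether the depot formulation is better. The protocol would nevertheless have told the ethics board, funders and readers to expect a 90% chance of detecting that difference.

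**Working it through.** **Inputs.** From 14.2 and 14.4: p = 0.30 and 0.45, difference 0.15, two-sided 5%, 45 per arm, within-patient correlation ρ = 0.8, clinic correlation 0.025, m = 5 measures, 4 clinics. From 12.11 and 13: m = 24. From Table 1: two 24-week trials that report mean percentage negative.

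**1. The simple test reproduces.** The variance sum is 0.30×0.70 + 0.45×0.55 = 0.4575. For 80% power, n = (1.960 + 0.842)² × 0.4575 / 0.15² = 159.6, so 160 as stated. For 90% power the same formula gives 213.7.

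**2. The three-level figures do not reproduce per arm.** The variance factor is f = [1 + (m − 1)ρ]/m = 4.2/5 = 0.84.
- 80%: 159.6 × 0.84 = 134.1 per arm (stated: 34).
- 90%: 213.7 × 0.84 = 179.5 per arm (stated: 45).

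Pooling the variance or subtracting the clinic correlation (f = 0.815) gives 130 to 136 and 174 to 182. As m grows, f cannot fall below ρ, so the floor is about 0.8 × 160 = 128 per group, or 0.775 × 160 = 124 with the clinic term.

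Dividing by clinics does reproduce the plan: 134.1/4 = 33.5, so 34; 179.5/4 = 44.9, so 45. In Table 3, scenario 2 gives 159.6 × 0.6/4 = 23.9 (stated 24), scenario 7 gives 134.1/3 = 44.7 (stated 45) and scenario 8 gives 134.1/2 = 67.03 (stated 68).

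**3. SDs from Table 1.** SE = CI width/(2 × 1.96) and SD = SE/√(1/n₁ + 1/n₂).
- Depot trial, "35.1% vs 28.4% (6.7% (-0.1, 13.6", 215 and 213 patients: SE = 13.7/3.92 = 3.49 points, SD = 0.362.
- Implant trial, "31% vs 33.1% (-2.1 (-10.7, 6.2", 114 and 119 patients: SE = 16.9/3.92 = 4.31 points, SD = 0.329.

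Divided by p(1 − p), the squared SDs are 0.603 (p = 0.3175) and 0.497 (p = 0.3205). These correspond to correlations of about 0.59 (assuming 24 tests, a count Table 1 does not give for the depot trial; 0.57 with 12) and 0.49 (72 tests).

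**4. Power at 45 per arm.** For the plan's type of input, SD = √(0.4575 f/2). Then SE = SD × √(2/45), power = Φ(0.15/SE − 1.96), and the difference detectable with 80% power is 2.80 × SE.

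| Input | SD | SE | Power at 0.15 | Difference at 80% power |
|---|---|---|---|---|
| ρ 0.8, m 5 (plan) | 0.438 | 0.0924 | 37% | 0.26 |
| ρ 0.8, m 24 | 0.430 | 0.0907 | 38% | 0.25 |
| ρ 0.5, m 5 (Table 3, scenario 2) | 0.370 | 0.0781 | 48% | 0.22 |
| Table 1 depot SD | 0.362 | 0.0762 | 50% | 0.21 |
| Table 1 implant SD | 0.329 | 0.0694 | 58% | 0.19 |

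With the clinic term, scenario 2 rises to 50%. On the plan's inputs, 34 per arm gives 29%, not 80%.

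**5. If 45 meant per arm per clinic,** there would be 180 per arm. Power would be about 90% on the plan's inputs and 97.6% to 99.1% on the Table 1 SDs.

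**The case against.** A correlation is a planning assumption, and 0.8 is on the cautious side: replacing it with what Table 1 implies raises power. Table 3 scenario 2 (SD about 0.37) already covers the depot trial's spread. Changing 5 to 24 adds about 1 point. Even 24 is not wholly settled. Section 12.11a confines screens to clinic-visit days, and the clinic-visit row of the timeline, as extracted, shows only 14 visits after baseline. The Table 1 SDs come from other formulations, from US trials and from 24 weeks rather than 48. Missing-as-positive scoring is footnoted for the implant trial, but for the depot trial only for its responder outcome. The implant interval is also slightly asymmetric about its estimate.

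All of this stands, and it limits the point. A reader might infer that 0.8 is an error, that any power computed from it is wrong, or that the Table 1 SDs should simply replace it. The documents do not support these readings: 0.8 is unsourced but conservative, and printing only the Table 1 result would hide the plan's own 37%. Nor does the mismatch between 5 and 24 explain the shortfall. A reader might also take 45 per arm per clinic as the intended size and conclude that power is adequate. Section 14.4 and the registration target of 90 both give 45 per arm over all four clinics.

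None of these objections rescues the 90.0%.

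**Conclusion.** The claim of 90.0% power at 45 per arm is unsupported. On the inputs available in the documents, power for a 0.15 difference is about 37% to 58%, which is 32 to 53 points lower. The main cause is that figures matching a count per arm per clinic are used as totals per arm. The unsourced correlation decides where in the range the trial sits. The number of measures hardly matters.

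The result rests on a normal-approximation comparison of patient-level proportions, not on the planned mixed logistic model with its visit-by-treatment interaction. The software output is not in the documents, so the per-clinic explanation is inferred from the match in the numbers. The upper end of the range also assumes normality, equal SDs in the two arms and carry-over of SDs from 24 to 48 weeks. It should be read as plausible, not exact.

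**What to change.** - Rerun the calculation behind 14.2, Table 3 and 14.4. State whether the software returns patients per arm or per arm per clinic, and use 24 measures per patient. The rerun should cover scenarios 9 and 10, which are labelled 90% power but carry values that match 80% (41, the same as scenario 4, and 54).
- Give a source or rationale for the within-patient correlation. Show Table 1 (SD 0.33 to 0.36, correlation about 0.5 to 0.6) as a sensitivity range beside 0.8, not in place of it.
- Replace the 90% at N=90 with the resulting range, about 37% to 58% for a 0.15 difference, and state that 80% power holds only for a difference of about 0.19 to 0.26.

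The cost is rewording and a less favourable stated power; no patients or procedures are added. Whether to enlarge the trial instead is the sponsor's decision. For scale, 90% power at 0.15 needs about 180 per arm on the plan's inputs, or 102 to 123 per arm on the Table 1 SDs.

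### Table 3's two 90%-power scenarios carry 80%-power sizes, scenario 5's input and output disagree, and the sizes appear to be per clinic, so the below-70-per-group claim fails

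*Combined protocol and SAP*

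**What the plan says.** Section 14.2 sizes the opioid-positivity comparison with a three-level mixed model (repeated measures within patients within clinics, patients randomised). Table 3 varies the inputs over ten scenarios and reports a row labelled "Sample size per group": 34, 24, 37, 41, 42, 38, 45, 68, 41, 54. From this the text concludes that the analysis "demonstrates that the upper range of sample sizes is consistently less than 70 per group".

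The power row reads "Power 80 80 80 80 80 80 80 80 90 90", so only scenarios 9 and 10 are set at 90%. The comparator proportion is 0.3 throughout, except for 0.1 in scenario 5 and 0.6 in scenario 6. The Level 1 correlation is 0.99 in scenarios 3 to 6, 9 and 10, 0.5 in scenario 2, and 0.8 in the others.

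Section 14.2 also says that an ordinary Z-test with unpooled variance would need 160 patients per group for the same difference.

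Section 14.4 adopts 45 patients per group over four clinics for 90.0% power, where the "RFWs proportions are 0.3 and 0.45, respectively", the correlations are 0.8 and 0.025, and "the 2-sided test is performed at the 5% significance level". Section 1.1 gives a target sample size of 90.

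**The concern.** Power cannot rise from 80% to 90% with every other input fixed and leave the sample size unchanged, yet scenarios 4 and 9 show exactly that. Scenario 5 moves in the wrong direction: a comparator proportion of 0.1 instead of 0.3 lowers the binomial variance, so the size should fall from 41, but it rises to 42. The table also behaves as if its sizes were per clinic: with the other inputs fixed, size times clinics is constant at 34 × 4 = 136, 45 × 3 = 135 and 68 × 2 = 136 (scenarios 1, 7 and 8).

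Table 3 is the protocol's stated evidence that the sample size is robust to its assumptions. If its 90% rows are really 80% rows, the upper bound is understated. If its unit is per clinic, the bound does not describe patients per arm at all, and the same question reaches the 45 per group in section 14.4.

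**Working it through.** **Inputs.** All come from Table 3, its footnote and section 14.4: two-sided alpha 0.05 (z = 1.960); power 80% or 90% (z = 0.842 or 1.282); difference 0.15; m = 5 measures per patient; correlations r1 (Level 1) and r2 (Level 2); number of clinics k; 1:1 allocation. Table 3 shows no dropout allowance and none is added.

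**Step 1: the contradiction needs no model.** Scenarios 4 and 9 share comparator 0.3, r1 = 0.99, r2 = 0.001, k = 4 and m = 5. Going from 80% to 90% power should multiply the size by (1.960 + 1.282)² / (1.960 + 0.842)² = 1.34. The protocol shows this response elsewhere: scenario 1 is 34 at 80%, and section 14.4 has the same inputs at 90% with 45, a ratio of 1.32. Scenarios 4 and 9 show a ratio of 1.00.

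**Step 2: a formula that fits the table.** Take the two-proportion size N0, multiply by F = [1 + (m − 1)r1 − m·r2]/m, divide by k and round up. The protocol gives no formula, so three variance forms were tried, with p̄ the mean of p1 and p2:
- Fleiss: N0 = [1.960√(2p̄(1 − p̄)) + z√(p1(1 − p1) + p2(1 − p2))]² / 0.15²
- Pooled: N0 = (1.960 + z)² · 2p̄(1 − p̄) / 0.15²
- Unpooled: N0 = (1.960 + z)² · [p1(1 − p1) + p2(1 − p2)] / 0.15²

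For 0.30 against 0.45 at 80% power the unpooled form gives 159.6, which is the protocol's own 160.

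| Scenario | Power | k | F | Fleiss | Pooled | Unpooled | Printed |
|---|---|---|---|---|---|---|---|
| 1 | 80% | 4 | 0.815 | 33.1 | 33.3 | 32.5 | 34 |
| 2 | 80% | 4 | 0.575 | 23.3 | 23.5 | 22.9 | 24 |
| 3 | 80% | 4 | 0.892 | 36.2 | 36.5 | 35.6 | 37 |
| 4 | 80% | 4 | 0.991 | 40.2 | 40.5 | 39.5 | 41 |
| 5 | 80% | 4 | 0.991 | 24.7 | 25.0 | 24.0 | **42** |
| 6 | 80% | 4 | 0.991 | 37.6 | 37.9 | 36.9 | 38 |
| 7 | 80% | 3 | 0.815 | 44.1 | 44.4 | 43.4 | 45 |
| 8 | 80% | 2 | 0.815 | 66.2 | 66.6 | 65.0 | 68 |
| 9 | 90% | 4 | 0.991 | 53.7 | 54.2 | 52.9 | **41** |
| 10 | 90% | 3 | 0.991 | 71.6 | 72.3 | 70.6 | **54** |

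Rounded up, the Fleiss and pooled forms return scenarios 1 to 4, 6 and 7 exactly and give 67 for scenario 8 (68 printed). The unpooled form is one lower on the six matched rows and two lower on scenario 8. For section 14.4 (90%, F = 0.815, k = 4) they give 44.2, 44.6 and 43.5, so 45, 45 and 44 against the stated 45.

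**Step 3: scenarios 9 and 10.** At 90% power they need 53 to 55 and 71 to 73. At 80% the Fleiss form gives 40.2 and 53.6, which round up to the printed 41 and 54. Fleiss power at the printed sizes, taken per clinic, is 80.8% and 80.3%.

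**Step 4: scenario 5.** The variance sum for 0.10 against 0.25 is 0.09 + 0.1875 = 0.2775; for 0.30 against 0.45 it is 0.21 + 0.2475 = 0.4575. Scaling scenario 4 gives 41 × 0.2775/0.4575 ≈ 25. A size of 42 would fit a comparator of about 0.35 or 0.50.

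**Step 5: the unit.** No row fits without dividing by k. The protocol's own Z-test figure points the same way. With r1 = 0.99, five measures add almost nothing to one (F = 0.991), so scenario 4 should need about 160 × 0.991 ≈ 159 per arm. The printed 41 is about a quarter of that, and 41 × 4 = 164.

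As totals per arm, the smallest requirement is scenario 2, 24 × 4 = 96. The largest are scenarios 9 and 10, about 212 to 217 each.

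**Step 6: consequence for section 14.4.** With 45 per arm per clinic, N/F = 180/0.815 = 220.9 and Fleiss power is Φ[(0.15√220.9 − 1.960√0.46875)/√0.4575] = Φ(1.31), about 90.5%. With 45 per arm in total, N/F = 45/0.815 = 55.2 and power is Φ(−0.34), about 37%.

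**The case against.** The formula is inferred by fitting the table. The protocol names only the software, and the fit misses scenario 8 by one. Exact replacement values therefore cannot be dictated from outside; only ranges and a rerun are justified. That stands.

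The adopted 45 per group does not come from scenarios 5, 9 or 10. On the table's own scale it reproduces at its stated 90% power. That also stands: the three row errors damage the robustness claim, not the calculation of the 45.

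A reader might infer three stronger things that the documents do not support:
- That scenario 5 helps to break the bound. It does not: if its input is right, its size falls to about 25. Scenario 9, at about 54, does not break it either. On the printed scale only scenario 10 does, and only by about 1 to 3.
- That 42 is the wrong cell in scenario 5. The input of 0.1 could equally be the slip.
- That the trial is shown to have 37% power. That figure follows if the per-clinic reading is correct and 45 is a total per arm. The first is a strong inference from the arithmetic that the investigators need to confirm against the software output.

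None of this explains two identical sizes at different power.

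**Conclusion.** Table 3 is wrong as written. That scenario 9 conflicts with scenario 4 is certain from the table alone. That scenario 10 also carries an 80% value, with a 90% requirement of about 71 to 73 against 54 printed, rests on the fitted formula, but all three two-sided variance forms put it above 70. Scenario 5 is internally inconsistent, with the faulty cell undetermined.

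The statement that all sizes stay below 70 per group therefore fails narrowly on the printed scale, through scenario 10 only. If the sizes are per clinic per arm, as the arithmetic indicates, it fails in every scenario, and the unit becomes the more serious matter: the power in section 14.4 would be about 37% for 45 per arm in total instead of 90%. These figures assume m = 5, the stated correlations and no dropout.

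**What to change.** Rerun all ten scenarios in the original software and keep the output on file. Replace scenarios 9 and 10 with their 90% values. Reconcile scenario 5 by checking whether the comparator proportion or the size was mistyped. State in the table whether each size is per clinic per arm or per arm in total. Withdraw the below-70 sentence or restate it on that unit, and restate the power in section 14.4 on the same unit.

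The rerun and the text corrections are cheap and need no new data. If the per-clinic unit is confirmed, the cost is larger: by the fitted formula, 90% power needs about 174 to 178 per arm in total, against the 45 planned. The investigators would then have to revise either the target of 90 or the power claimed for it, by formal amendment if the sample size changes (section 25).
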